14.3.5 Analysis of primary efficacy endpoint

The primary endpoint, change from baseline to Week 8 in EASI, will be analysed for the full analysis set and for the per protocol analysis set. The per protocol analysis is regarded as supportive.

For the analysis of the change from baseline to Week 8 in EASI, data collected after permanent discontinuation of IMP or after initiation of rescue medication will not be included in the analysis. Missing data at Week 8 will be imputed using the MMRM predicted values from the below specified model for repeated measurements.

The MCP-Mod approach (see e.g. [EMA Qualification Opinion of MCP-Mod](#) or [Bretz et al. 2005](#) for further details of the framework) will be used to guide dose selection. The dose-response relationship for the continuous endpoint Change from baseline to Week 8 in EASI will be modelled by the following 3 identified candidate models. These candidate models are selected based on the expected dose-response.

Linear in log: $E_0 + \delta \times \log(d + c)$,

E_{max}: $E_0 + E_{\max} \times d / (ED_{50} + d)$,

Sigmoid E_{max}: $E_0 + E_{\max} \times d^h / (ED_{50}^h + d^h)$,

where d is the dose (incl. vehicle), E_0 is the efficacy offset (anticipated vehicle effect), E_{\max} is the asymptotic maximum effect, ED_{50} is the half-life value of E_{\max} , h is the steepness at ED_{50} , δ is the slope parameter, and c is a fixed offset parameter.

The models will be adjusted for the stratification variables region and disease severity (baseline vIGA-AD of 2, 3, and 4). The model parameters (ED_{50} , h) will be prespecified a priori by suitable guesses based on data from Japan Tobacco's dose-ranging trial QBA2-1 (Nakagawa et al. 2018). Akaike's Information Criteria will be used as the goodness-of-fit criterion that will drive the selection of the dose-response model that fits data best while controlling the family-wise error rate at 5%. Based on the selected model, the dose-response relationship will be estimated and presented with 2-sided 95% CI. If none of the candidate models converge, other possibilities of models and goodness-of-fit criteria will be explored. The dose-response modelling will be performed on both the total population and subjects having a baseline vIGA-AD of 3 or 4, in order to further explore heterogeneity in the disease population.

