In addition to the dose-response modelling approach, the continuous endpoint will be analysed using an MMRM on the post baseline responses up to Week 8 with an unstructured covariance matrix, Kenward-Roger approximation to estimate denominator degrees of freedom, and the mean modelled as follows:

Change from baseline in EASI

$$= \text{treatment} \times \text{visit} + \text{baseline EASI} \times \text{visit} + \text{region} + \text{baseline vIGA-AD}$$

The estimates will be presented with nominal p-values and 95% CI at each visit. The primary comparison between each delgocitinib dose and vehicle will be at Week 8.

Sensitivity analysis will be performed as applicable in order to assess the robustness of results of the primary analysis with respect to the retrieved data at Week 8 and assumptions regarding missing data. This will be described in further detail in the statistical analysis plan.

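### The 95% CI for the dose-response curve ignores the AIC model selection and, under some plausible curves, covers well below 95% at 1, 3 or 8 mg/g

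*Combined protocol and SAP*

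**What the plan says.** Section 14.3.5 names three candidates for the primary endpoint: linear in log dose with a fixed offset c, Emax, and sigmoid Emax. Akaike's "Information Criteria will be used as the goodness-of-fit criterion that will drive the selection of the dose-response model that fits data best", with a 5% family-wise error rate. Then: "Based on the selected model, the dose-response relationship will be estimated and presented with 2-sided 95% CI". No interval formula is named.

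On the shape parameters the section points two ways. ED50 and h "will be prespecified a priori by suitable guesses based on data from" an earlier dose-ranging trial, yet it adds: "If none of the candidate models converge, other possibilities of models and goodness-of-fit criteria will be explored". With ED50, h and c all fixed, every candidate is linear in its remaining parameters and can always be solved. The second sentence therefore suggests that ED50 and h are estimated.

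Also relevant from section 14.3.5:
- "Missing data at Week 8 will be imputed using the MMRM predicted values from the below specified model for repeated measurements".
- "The dose-response modelling will be performed on both the total population and subjects having a baseline vIGA-AD of 3 or 4".
- For the separate MMRM analysis: "The estimates will be presented with nominal p-values and 95% CI at each visit".

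The sensitivity analyses there address retrieved Week 8 data and missing data, not model choice. Section 14.3.6 carries the modelling over to EASI75 and vIGA-AD treatment success.

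**The concern.** The three candidates have two, three and four mean parameters. AIC penalises parameters, so it often prefers a simpler model than the true one. The interval from that model is then too narrow and sometimes off-centre, because it treats the chosen form as known in advance. The 5% family-wise rate limits false dose-response signals and does nothing for interval coverage.

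The curve is the main output for the primary objective, and the section says MCP-Mod will guide dose selection. The low and middle strengths, where one judges whether less drug suffices, are where coverage falls most. A reader would take the band as 95%.

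**Working it through.** **1. The plan's own figure.** Section 14.1: difference 7, SD 9, two-sided 5%. With n=50 per arm, SE = 9 x sqrt(2/50) = 1.80, and power = Phi(7/1.80 - 1.96) = Phi(1.93) = 97.3%, which meets the stated minimum of 95%. With n=35 and n=40 it is 90.2% and 93.6%, in line with about 90%. The plan states no coverage figure beyond the nominal 95%.

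**2. Inputs.**
- From the documents: doses 0, 1, 3, 8 and 20 mg/g; n=50 per arm; SD 9; difference 7; the three model forms.
- Assumed, because the documents give no values: the 7 points sit at 20 mg/g; c is 1 or 0.2; the interval is delta-method; ED50 and h are estimated (ED50 within 0.02-30, h within 0.5-10).
- Six assumed true curves: Emax with ED50 0.5, 2 and 5; sigmoid with ED50 3 and h 3 or 1.5; log-linear. With two values of c this makes 12 scenarios, each with 6000 trials.

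**3. Formulas.** AIC = N log(RSS/N) + 2k, with k the number of estimated parameters. The interval at dose d is the fitted mean plus or minus t x sqrt(g'Vg). Here g is the gradient of the selected model in its parameters and V is their estimated covariance.

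**4. Coverage of the true mean over the 12 scenarios.**

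| Dose (mg/g) | 1 | 3 | 8 | 20 |
|---|---|---|---|---|
| Selected-model CI | 69-94% | 82-92% | 75-95% | 90-95% |

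The true model, always fitted, covered 93-97% at every dose, so neither the delta method nor the sample size explains the loss.

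At 1 mg/g, seven scenarios give 89-94% and five give 69-85%: the steep sigmoid (77% with c=1, 69% with c=0.2) and, with c=0.2 only, sigmoid h=1.5 (75%), Emax ED50 0.5 (83%) and Emax ED50 5 (85%). At 8 mg/g coverage drops below 92% only under the sigmoid curves (75-90%).

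**5. A second, separately coded set with other curves.** These runs used AIC selection alone; the contrast test passes in 99-100% of trials at this effect. The last column repeats the selection in each bootstrap resample (600 trials x 500 resamples). Coverage is shown at 1 / 3 / 8 mg/g.

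| True curve | Selected: log-linear / Emax / sigmoid | Selected-model CI | True model always fitted | Bootstrap |
|---|---|---|---|---|
| Emax ED50 1, c=1 | 35 / 57 / 8% | 90.5 / 80.2 / 94.2% | 95.5 / 95.1 / 95.5% | 96.2 / 96.8 / 94.0% |
| Sigmoid ED50 5, h 3, c=1 | 43 / 12 / 45% | 90.1 / 69.7 / 83.9% | 96.8 / 95.4 / 97.2% | 94.8 / 94.5 / 95.3% |
| Sigmoid ED50 3, h 2, c=0.2 | 47 / 22 / 31% | 67.2 / 92.3 / 85.5% | 97.2 / 95.6 / 97.5% | 95.2 / 97.5 / 96.3% |
| Log-linear, c=1 | 80 / 12 / 7% | 94.3 / 92.3 / 94.4% | 95.0 / 94.8 / 94.8% | 95.7 / 97.0 / 94.0% |

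The second row shows the mechanism. The true family is chosen in only 45% of trials, and the median width at 3 mg/g is 3.0 points, against 4.9 when the true family is always fitted.

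**6. Variations (coverage at 1, 3 and 8 mg/g).**
- Contrast step added: 69-94%, 82-92%, 75-96%. It passed in 98-100% of trials.
- 15% of Week 8 values missing and imputed: 71-91%, 81-89%, 77-94%. With 25% missing: 72-90%, 78-89%, 74-92%. Both rates are assumed, with values missing completely at random.
- 35-40 per arm, the subgroup example in section 14.1: 67-94%, 83-93%, 78-96%.
- Effect of 4 instead of 7 (second set of curves): the loss shrinks but remains. At 3 mg/g, sigmoid ED50 5, h 3 gives 78-80% and Emax ED50 1 gives 85-86%.
- ED50 and h held at guessed values (three assumed sets): 49-91% at 1 mg/g and 70-94% at 3. This mixes wrong guesses with selection, so it shows only that the other reading of the text is no escape.

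**The case against.** **The method is unspecified rather than wrong.** The protocol names no formula, and section 14.3.12 finalises the SAP before unblinding, so a bootstrap is not excluded. That is true. But the text bases the interval on the selected model and mentions no allowance for selection.

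**The curves and c are invented.** Four of the five poor results at 1 mg/g need c=0.2, and the fifth needs a steep sigmoid. So the figures are ranges under assumptions, not predictions. Still, every true curve comes from the plan's own candidate families. Coverage is near nominal when the truth is log-linear and c matches.

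**The error in EASI points is small.** In a repeat of the 12 scenarios, the selected curve's bias was at most 0.66 points. Its root mean squared error at active doses was 0.73-1.36, against 1.27 for a plain arm mean (9/sqrt(50)). When the interval missed, the median miss was 0.15-0.65 points. This stands: the point estimate is good, and only its stated precision is wrong.

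**Safeguards exist.** The MMRM gives selection-free intervals at each dose, p-values are nominal (section 14.3.4), and no rule uses the curve's interval. This limits the harm but does not correct the band.

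**Conclusion.** The concern holds. As written, the curve's 95% interval conditions on a model chosen from the same data. Over the 12 assumed scenarios its coverage is 69-94% at 1 mg/g, 82-92% at 3 and 75-95% at 8; at 20 mg/g it is close to nominal. Separately coded repeats of those scenarios gave nearly the same ranges, and the other set of curves gave roughly 67-95% at 1, 3 and 8 mg/g.

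The size depends on the true curve, c and the delta-method assumption. The region and severity covariates and the binary endpoints were not simulated. This is a should-fix point: it misstates precision on the primary objective's main display, but leaves the MMRM comparisons and the AIC point estimate intact.

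**What to change.** State in the SAP:

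1. ED50 and h are estimated in the modelling step; the prior guesses serve only the contrast test.
2. The curve's interval, and any model-based difference from vehicle, is a percentile bootstrap interval. Subjects are resampled within arm, and each resample repeats the Week 8 MMRM imputation, the covariate-adjusted fits and the AIC selection. Parameter bounds and the handling of failed resamples should be stated.
3. The AIC-selected model remains the point estimate.
4. The MMRM dose-group estimates and intervals are overlaid on the plot.

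With 0, 15 and 25% missing, this bootstrap covered 92-97% at 1 mg/g, 94-98% at 3, 91-97% at 8 and 92-96% at 20. Two parts are essential. Without repeating the imputation, coverage at 25% missing was 90-94%, 90-96%, 86-93% and 87-93%. With ED50 and h held fixed, the bootstrap covered only 45-97% at 1 mg/g.

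Repeating the contrast test in each resample and extending the method to the binary endpoints of section 14.3.6 would be reasonable. Neither was tested, and since the test passes in 98-100% of trials the first should matter little.

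**Cost.** SAP wording, code and computing time; no change to data or sample size. Section 7.4 puts the modelling in R and everything else in SAS, so the MMRM must be linked to, or rewritten for, the resampling loop. The work repeats for the per protocol set and the vIGA-AD 3 or 4 subset. Intervals widen; median widths over the 12 scenarios, in EASI points:

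| Dose (mg/g) | 1 | 3 | 8 | 20 |
|---|---|---|---|---|
| Selected-model CI | 2.8 | 2.3 | 2.8 | 3.8 |
| Bootstrap | 4.0 | 3.8 | 3.5 | 4.1 |

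All stay below the width for a single arm mean, 2 x 1.97 x 9/sqrt(50) = 5.0.

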14.3.6 Analysis of secondary efficacy endpoints

The secondary endpoints, vIGA-AD TS and EASI75 at Week 8, and time to vIGA-AD TS will be analysed for the full analysis set and for the per protocol analysis set. The per protocol analysis is regarded as supportive.

For the analysis of the secondary binary endpoints, subjects who initiate rescue medication before Week 8 or permanent discontinue IMP and have no retrieved data at Week 8, will all be considered non-responders.

The dose-response modelling approach suggested for the primary endpoint will also be applied for the binary secondary endpoints, vIGA-AD TS and EASI75 at Week 8.

In addition to the dose-response modelling approach, difference in response rates between the delgocitinib doses and vehicle will be analysed separately for each of the dose groups using the Cochran-Mantel-Haenszel test stratified by region and disease severity. The null hypothesis of no difference in response rates between the delgocitinib doses and vehicle will be tested against the 2-sided alternative that there is a difference. Furthermore, a shift table for the vIGA-AD will be presented for baseline to Week 8 per treatment group.

The time to vIGA-AD TS response is defined as the time from baseline to first assessment of a vIGA-AD TS. Subjects will be censored at the date of the last assessment visit or at initiation of rescue medication, whichever occurs first. Kaplan-Meier curves of time to vIGA-AD TS will be estimated and presented by treatment for the full analysis set. Treatment groups will be compared using a 2-sided log-rank test stratified by region and baseline vIGA-AD.

Sensitivity analysis will be performed as applicable in order to assess the robustness of results of the primary analysis with respect to the retrieved data at Week 8, use of rescue medication, and assumptions regarding missing data. This will be described in further detail in the statistical analysis plan.

14.3.7 Analysis of other endpoints

To support the primary and secondary endpoints, EASI50 at Week 8 and EASI90 at Week 8 will be analysed and presented for the full analysis set. Both endpoints will be analysed using the Cochran-Mantel-Haenszel approach as described for the analysis for the secondary binary endpoints.

To support the primary and secondary endpoints on severity and extent of AD, at least 75% reduction in SCORAD score (SCORAD75) at Week 8, SCORAD50 at Week 8, and the change from baseline to Week 8 in SCORAD score will be analysed and presented for the full analysis set. SCORAD50 and SCORAD75 will be analysed using the Cochran-Mantel-Haenszel approach as described for the analysis for the secondary binary endpoints, and the change from baseline to Week 8 will be analysed using the MMRM approach as described for the analysis for the primary endpoint.

14.3.7.1 Analysis of patient-reported outcomes

The PROs POEM, DLQI, PGI-S, PGI-C, SF-36, EQ-5D-5L, WLQ and TSQM will be summarised by treatment group and visit using descriptive statistics. The summaries will be presented for the full analysis set.

The ADSD and Eczema-related Sleep NRS collected in the eDiaries on a daily basis (all individual symptoms) will be summarised over time by treatment group using descriptive statistics. The summaries will be presented for the full analysis set.

The daily diary recordings of the ADSD will be derived into discrete weekly endpoints based on calendar time (with the exception of Week 8) from baseline visit, i.e. the endpoints represent the nominal week and are not directly related to the actual visit in contrast to other visit-based assessments. The algorithm for deriving the endpoints at each time point is described as follows: baseline weekly average will be defined by average of measurements from Day -7 to Day -1, Week 1 weekly average will be defined by the average of measurements from Day 1 to Day 7, Week 2 weekly average will be defined by the average of measurements from Day 8 to Day 14 and so on, until Week 7. Week 8 will be calculated based on the 7 days preceding the Week 8 visit. A minimum of 4 ADSD scores out of the 7 days are required to calculate the average score. This will be derived for each individual symptom, respectively. The same derivation rules will be applied for the Eczema-related Sleep NRS.

In the subgroup of subjects with a baseline worst pruritus (one of the symptoms captured in the ADSD) (weekly average) score of ≥ 4 , the proportion of subjects with reduction in worst pruritus (weekly average) of ≥ 4 from baseline to Week 8 will be summarised by treatment group and analysed using the Cochran-Mantel-Haenszel approach as described for the analysis of the secondary binary endpoints.

In the subgroup of subjects with a baseline DLQI score of ≥ 4 , the proportion of subjects with a reduction in DLQI score of ≥ 4 at Week 8 will be summarised by treatment group and analysed as described using the Cochran-Mantel-Haenszel approach for the analysis of the secondary binary endpoints. In addition, the proportion of subjects achieving a DLQI score of 0 or 1 at Week 8 will be presented.

In the subgroup of subjects with a baseline POEM score of ≥ 4 , the proportion of subjects with a reduction in POEM score of ≥ 4 at Week 8 will be summarised by treatment group and analysed using the Cochran-Mantel-Haenszel approach as described for the analysis of the secondary binary endpoints.

The change from baseline to Week 8 in ADSD (weekly average for each individual symptom), Eczema-related Sleep NRS (weekly average), POEM, DLQI, SF-36, EQ-5D-5L and WLQ will be summarised by treatment group and domain, where applicable, and analysed using the MMRM approach as described for the analysis of the primary endpoint.

The TSQM at Week 8 will be summarised by treatment group and domain and compared between treatments using an analysis of variance model including treatment, region and baseline vIGA-AD as factors.

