Secondary endpoints	
 Validated Investigator Global Assessment scale for Atopic Dermatitis (vIGA-AD) score of 0 (clear) or 1 (almost clear) with ≥ 2-step improvement (vIGA-AD treatment success [TS]) from baseline to Week 8. EASI75 at Week 8. Time to vIGA-AD TS.
Final collection of data for the primary endpoint	Week 8.
Trial design	
The trial is designed as a double-blind, multi-centre, randomised, 5-arm, vehicle-controlled, parallel-group trial in which adult subjects with mild to severe AD will be treated with delgocitinib cream (1, 3, 8, 20 mg/g) or delgocitinib cream vehicle for 8 weeks.
 
The trial consists of a screening period, a treatment period, and a follow-up period.

Screening period

The screening period has a minimum duration of 2 weeks and a maximum duration of 4 weeks. At the screening visit, the subjects' eligibility to enter the trial will be checked. The subjects will receive training in completion of an electronic diary (eDiary). Furthermore, the subjects will be asked to fill out patient-reported outcome measures (PROs).

[figure not shown]
Treatment period

At baseline (Day 1), subjects' eligibility to enter the trial will be confirmed and, if still eligible, the subjects will be randomised to 1 of the 5 treatment groups. The randomisation will be stratified by the severity of AD according to vIGA-AD (mild, moderate, and severe) and region (North America and Australia).

The first application of the investigational medicinal product (IMP) will occur at the trial site at baseline (Day 1). The subsequent IMP applications will be performed by the subjects at home twice daily for 8 weeks. During the treatment period, the subjects will be required to return to the trial site for the visits scheduled at Weeks 1, 2, 4, 6 and 8. The last IMP application will occur before the subjects attend the visit scheduled at Week 8.

Follow-up period

All subjects will attend a follow-up visit approximately 2 weeks after the last IMP application for assessment of safety.

Main assessments	Investigator efficacy assessments:
------------------	-------------------------------------------

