7.1 Overall trial design

This is a phase 2b double-blind, multi-centre, randomised, 5-arm, vehicle-controlled, parallel-group trial. The trial is designed to establish a dose-response signal and to investigate the efficacy and safety of delgocitinib cream in the treatment of adult subjects with mild to severe AD. The trial design is illustrated in [Panel 1](#).

The trial consists of a screening period, a treatment period and a follow-up period.

Screening period - between 2 and 4 weeks prior to baseline visit (Day 1)

The screening period has a minimum duration of 2 weeks and a maximum duration of 4 weeks.

At the screening visit, the subjects' eligibility to enter the trial will be checked. Trial-specific measurements will be performed as outlined in [Section 11](#).

The subjects will receive training in completion of an eDiary at the screening visit and will be given an electronic device to record certain PROs. Furthermore, to complete training of the eDiary and as an opportunity to fill out PROs before the treatment period, subjects will be asked to complete PROs at the screening visit. Completion of the eDiary will be initiated at the latest 1 week prior to the baseline visit (Day 1).

All subjects must use an emollient twice daily (or more, as needed) for at least 14 days before Day 1; this background treatment should preferably be an additive free, basic bland emollient. After randomisation on Day 1, emollients must not be used concomitantly with delgocitinib cream or delgocitinib cream vehicle on lesional skin. Subjects may however continue to use their background emollient treatment on non-lesional skin throughout the trial (including safety follow-up).

Treatment period - 8 weeks

At baseline (Day 1), subjects' eligibility to enter the trial will be confirmed and, if still eligible, subjects can be randomised 1:1:1:1:1 to one of the following 5 treatment groups in a 1:1:1:1:1 ratio: delgocitinib cream 1, 3, 8, 20 mg/g or delgocitinib cream vehicle.

The subjects will apply the IMP (delgocitinib cream 1, 3, 8, or 20 mg/g or delgocitinib cream vehicle) twice daily for 8 weeks. The first application of the IMP will occur at the trial site on

Day 1 after all baseline assessments have been carried out. The subsequent IMP applications will be performed by the subjects at home.

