11.7 Other assessments

11.7.1 Patient-reported outcomes (PROs)

Each subject must make individual assessments relating to their perception of their disease and quality of life. These will be performed prior to the investigator performing his/her efficacy assessments. At the screening visit, the subject's eligibility needs to be established before the PROs can be completed.

The subjects will receive an eDiary device and eDiary training, as well as complete all of the PROs (except TSQM), at the screening visit. Completion of the eDiary will be initiated at the latest 1 week prior to the baseline visit (Day 1).

Two PROs will be assessed daily using an eDiary:

- ADSD.
- Eczema-related Sleep NRS.

The subjects must complete the eDiary each day in the evening, and compliance with the eDiary completion will be reviewed by the trial site staff throughout the trial. The eDiary should be returned to the trial site as outlined in the schedule of trial procedures (Section 4).

In addition, 8 PROs will be completed on an electronic device by the subjects at the trial sites at the visits specified in the schedule of trial procedures (Section 4). The PROs will be completed in the following order:

- POEM.

- DLQI.
- PGI-S.
- PGI-C.
- SF-36.
- EQ-5D-5L.
- WLQ.
- TSQM.

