11.7.1.2 Eczema-related Sleep Numeric Rating Scale (Eczema-related Sleep NRS)

Eczema-related Sleep NRS is a scale developed by LEO. Subjects will rate how much their eczema interfered with their sleep the previous night using an 11-point NRS (0 indicating it 'did not interfere' and 10 indicating that it 'completely interfered'). Subjects will complete the Eczema-related Sleep NRS as part of an eDiary each day in the evening at the latest from Week -1 to Week 8.

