14.3.7.2 Efficacy over time

To further explore possible early onset of effect and general efficacy over time, the following endpoints will be evaluated at each scheduled assessment up to Week 6 or each week up to Week 7:

- vIGA-AD TS at each scheduled assessment until Week 6.
- EASI75 at each scheduled assessment until Week 6.
- Change in SCORAD from baseline to each scheduled assessment until Week 6.
- Change from baseline to each week through Week 1 to 7 in ADSD (weekly average for each individual symptom).
 - Reduction of worst pruritus (one of the symptoms captured in the ADSD) (weekly average) of ≥ 4 points from baseline to each week through Week 1 to 7 among subjects with baseline worst pruritus (weekly average) of ≥ 4 .
- Change from baseline to each week through Week 1 to 7 in Eczema-related Sleep NRS (weekly average).
- Change in DLQI score from baseline to each scheduled assessment until Week 6.
- Reduction in DLQI of ≥ 4 from baseline to each scheduled assessment until Week 6 among subjects with baseline DLQI ≥ 4 .

For the binary endpoints, the same Cochran-Mantel-Haenszel test as for the Week 8 assessment will be applied. For the continuous endpoints, the repeated measurements model already described previously for the Week 8 assessments facilitates that the p-values, treatment differences, and 95% CIs can be derived for each visit up to Week 6 (or Week 7 for the change in ADSD (weekly average for each individual symptom) and Eczema-related Sleep NRS [weekly average]).

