Section 14.3.1 Disposition of subjects	The sentence on presentation of reasons for permanent discontinuation of IMP and withdrawal from trial has been revised. Reasons will not be presented by last visit attended.	Reasons for permanent discontinuation of IMP and withdrawal from trial will be presented by treatment group only.
Section 14.3.4 Testing strategy Section 14.3.6 Analysis of secondary efficacy endpoints Section 14.3.7.2 Efficacy over time	Change of treatment success abbreviation from vIGA-AD 0/1 to vIGA-AD TS.	To avoid misunderstandings between an vIGA-AD score of 0 (clear) or 1 (almost clear) and vIGA-AD treatment success defined as an IGA score of 0 (clear) or 1 (almost clear) with at least a 2-step improvement.
Section 14.3.7.1 Analysis of patient-reported outcomes	PGI-C has been added to the list of PROs to be summarised by treatment group and visit using descriptive statistics. Time interval calculations of weekly average of ADSD have been revised (e.g. baseline weekly average of ADSD will be defined	To reflect the addition of PGI-C assessment in the trial. The approach for calculation of weekly average has been revised since ADSD is completed in the evening

Section no. and name	Description of change	Brief rationale
	
by average of measurements from Day -7 to Day -1 instead of from Day -6 to Day 1) and text has been slightly revised.
 
The description of how to analyse PGI-S has been deleted.
	
throughout the trial.
 
PGI-S has been deleted as an endpoint and will only be summarised descriptively.

Section 14.3.9.1 Adverse events
	
It has been added that adverse events of special interest will be tabulated by treatment group and listed.
 
AEs leading to withdrawal from trial and AEs leading to-permanent discontinuation of IMP will be tabulated by treatment group. No narratives will be made for these AEs.
	
To clarify how adverse event of special interest will be summarised.
 
AEs leading to withdrawal from trial and AEs leading to permanent discontinuation of IMP, as well as AEs of special interest will be tabulated and listed as this is a more informative way of presenting data on these event types.

Section 14.3.9.4 Subject assessment of local tolerability
	
New section.
	
To describe statistical handling of the subject assessment of local tolerability.

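### The Week 1 Eczema-related Sleep NRS average includes one night before the first application, which dilutes a true early effect by 14% (complete diary) to 25% (four entries)

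*Combined protocol and SAP*

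**What the plan says.** Section 11.7.1.2 sets the recall period of the scale: "Subjects will rate how much their eczema interfered with their sleep the previous night using an 11-point NRS". Section 11.7.1 sets the time of entry: "The subjects must complete the eDiary each day in the evening". Section 7.1 places the first application at the trial site on "Day 1 after all baseline assessments have been carried out".

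Section 14.3.7.1 defines the diary weeks for the ADSD. Baseline is Day -7 to Day -1, and "Week 1 weekly average will be defined by the average of measurements from Day 1 to Day 7". Later weeks follow in seven-day blocks to Week 7, and Week 8 is the seven days before the Week 8 visit. At least four of seven entries are needed. It then adds: "The same derivation rules will be applied for the Eczema-related Sleep NRS".

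Amendment 1 (Appendix 7) gives the reason for these windows: "The approach for calculation of weekly average has been revised since ADSD is completed in the evening". That reason concerns the ADSD and the time of day. Nothing is said about the Sleep NRS or its recall period.

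Section 14.3.7.2 analyses the weekly Sleep NRS change from Week 1 onwards, and the stated aim of that section begins "To further explore possible early onset of effect and general efficacy over time".

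**The concern.** An evening entry that rates the previous night lags the calendar by one night. The windows were set with the ADSD in mind and carried over to the Sleep NRS without allowing for that lag. The first Week 1 entry then describes sleep that treatment cannot have affected. By randomisation its expected difference between arms is zero, so it pulls the Week 1 contrast towards no difference.

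Week 1 is the first point at which the Sleep NRS could show an early effect. An understated difference there could make onset look slower or weaker than it is, in a trial whose results are meant to inform phase 3 (Section 5.3).

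**Working it through.** **Timing.** An evening entry on Day d rates the night from the day before to Day d.

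| Entry | Night rated | Relative to first application | Window |
|---|---|---|---|
| Day -1 | Day -2 to Day -1 | before | Baseline |
| Day 1 | Day -1 to Day 1 | before | Week 1 |
| Day 2 | Day 1 to Day 2 | after | Week 1 |
| Day 7 | Day 6 to Day 7 | after | Week 1 |
| Day 8 | Day 7 to Day 8 | after | Week 2 |

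Only the Day 1 entry is misplaced. Weeks 2 to 8 contain no night before the first application.

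**Plan's own figure.** The plan gives no effect size, SD or power for the Sleep NRS. Its only power statement is for EASI (Section 14.1: difference 7, SD 9). It reproduces under the normal approximation: 97.3% with 50 per arm, and 90.2% and 93.6% with 35 and 40. It has no bearing here.

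**Dilution.** With n Week 1 entries including Day 1, one has expected difference 0 and n - 1 carry the mean treated-night difference D. The expected Week 1 difference is D × (n - 1)/n, a loss of 1/n.

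- n = 7: 1/7 = 14.3%
- n = 6: 1/6 = 16.7%
- n = 5: 1/5 = 20%
- n = 4: 1/4 = 25%
- Day 1 entry missing: 0%

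If all days are equally likely to be completed, the average loss is 1/7 = 14.3% at any completion rate. Baseline adjustment does not remove it. In a simulation with 50 per arm, an assumed constant difference of 1 point and a baseline covariate, the mean estimate was 0.859 under the current window and 1.002 for Day 2 to Day 8 (ratio 0.857, that is 6/7).

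**Illustrations under assumptions.**

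- True effect of 1.5 points from the first treated night: 1.5 × 6/7 = 1.29 instead of 1.50.
- Same effect building linearly over 14 nights: nights 1 to 6 average 1.5 × 3.5/14 = 0.375, and with the Day 1 entry included this becomes 0.375 × 6/7 = 0.32.
- If the treated-night contrast had 80% power at two-sided 5% and the SD were unchanged, power at factor 6/7 is Φ((1.960 + 0.842) × 6/7 - 1.960) = 67%. A starting power of 90% falls to 79%.

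**Loss of evaluable subjects if Day 1 is dropped.** With independent daily completion probability p, the subjects lost are those with Day 1 and exactly three of the other six days: p × 20 × p³ × (1 - p)³.

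| p | At least 4 of 7 | At least 4 of 6 | Lost (points) |
|---|---|---|---|
| 0.9 | 99.7% | 98.4% | 1.3 |
| 0.8 | 96.7% | 90.1% | 6.6 |
| 0.7 | 87.4% | 74.4% | 13.0 |

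**Net effect on precision.** Compare (effect fraction ÷ baseline-adjusted residual SD) × √(evaluable share), new over current. Take equal correlation ρ between all days, complete diaries and ρ = 0.5, in units of the daily variance:

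- Variance of the baseline mean: (1 + 6 × 0.5)/7 = 0.5714. Variance explained by baseline: 0.25/0.5714 = 0.4375.
- Residual variance, seven entries: 0.5714 - 0.4375 = 0.1339 (SD 0.366).
- Residual variance, six entries: (1 + 5 × 0.5)/6 - 0.4375 = 0.1458 (SD 0.382).
- Ratio: (1/0.382) ÷ (0.857/0.366) = 1.12.

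For ρ from 0.3 to 0.8 the ratio is about 1.12 at 100% completion, 1.11 at 90%, 1.09 at 80% and 1.05 at 70%.

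**Spill-over.** All weeks share one MMRM, so later estimates could move where data are missing. In 200 simulated trials per setting (assumed daily SD 2.2, effect 1.5, 18 to 20% dropout), the mean Week 8 shift was at most 0.002 points against a standard error of 0.31 to 0.38. This is negligible.

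**The case against.** The strongest reply is that the rule does what it says. Section 14.3.7.1 defines nominal calendar weeks, and Day 1 to Day 7 is the first of them. The dilution exists only relative to the mean over treated nights, a target the protocol does not name. That is fair as a description of the rule. But the section that uses the Week 1 value states onset as its purpose, and a night before treatment carries no information on onset.

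The consequences are also small. This is one time point of one exploratory endpoint with nominal p-values. The rule is the same in all arms, and the bias cannot create a false claim of onset. Early effect can also be seen in the daily diary summaries and in the Week 1 visit assessments, including SCORAD, which covers sleeplessness over the last three nights. All of this stands and limits the weight of the point. SCORAD is only a partial substitute, because sleep is one part of a total score.

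Finally, the precision gain depends on the correlation model. If correlation decays with time between days, the gain falls to about 1.10 at full completion, 1.06 to 1.07 at 80% and 1.02 to 1.03 at 70%. At 60% it becomes a slight loss (0.97 to 0.98), and even equal correlation gives about 1.00 there. The documents state no expected completion rate. This also stands: the case for the change is removal of the bias, and the precision gain is secondary.

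**Conclusion.** The concern holds. As written, the Week 1 Sleep NRS average contains one night before the first application. A true effect over the treated nights is understated in expectation by 1/n: 14.3% with a complete diary, 25% with four entries including Day 1, and nothing if Day 1 is missing. This rests on randomisation, on subjects rating the night the question asks about, and on the treated nights being the right reference for onset.

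It is a minor point worth correcting because correction is cheap. Under no effect there is no bias. Primary and secondary endpoints and the Sleep NRS windows for Weeks 2 to 8 do not contain the entry. Nothing is concluded about the ADSD, whose recall period is redacted. The conclusion concerns the rule in the protocol; no separate SAP text with a different derivation was available.

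**What to change.** State in the SAP that, for the Eczema-related Sleep NRS only, the Week 1 average uses the entries of Day 2 to Day 7 with at least four required, and that the Day 1 entry is not used. Leave the Sleep NRS baseline and Weeks 2 to 8 as they are, and make no change to the ADSD. Give the reason: evening entry with previous-night recall. Section 14.3.12 has the planned analyses reviewed on blinded data and the SAP finalised before the randomisation code is broken, which is the place to do this.

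The cost is one sentence and one derivation line, with no new data. Week 1 then rests on at most six entries and is built differently from the other weeks. Subjects with exactly four entries including Day 1 lose their Week 1 value, in the numbers tabulated above. In the simulation, 0.04 to 0.49 per 100 subjects left the MMRM because they had no other post-baseline value.

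Shifting the windows by one day costs more. If Weeks 1 to 7 move and Week 8 does not, the entries shared by Weeks 7 and 8 rise from 0, 1, 2, 3 to 1, 2, 3, 4 for Week 8 visits on Days 57, 56, 55, 54. If Week 8 moves too, it needs the evening entry of the visit day, but the eDiary is handed back at that visit (Panel 2), so at most six entries remain. Counting the Day 1 entry in baseline would also remove the dilution, but it would put an answer given after randomisation and first application into the baseline covariate.
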